 - HAQ response at 28 weeks after randomization and at w104
2. Radiographic progression: X-ray evolution at w52 and w104 compared to BL as reviewed and evaluated by the central team.
3. Side effects: (S)ARs from BL until w104
4. To evaluate the primary outcome using the DAS28ESR instead of the DAS28CRP.

Other secondary, exploratory outcome measures:

1. Clinical effectiveness:

A) In the randomized early insufficient responder population (w8-w32) with or without accelerated access to a six-month course of etanercept.

Effectiveness:

- AUC of DAS28CRP/DAS28ESR during 28 weeks after randomization
- Time to first remission during 28 weeks after randomization
- Sustained remission = remission for at least 24 weeks (BL-w104).
- Number of treatment changes, number of patients able to follow the protocol, number of patients using biologicals and/or GC at 28 weeks after randomization and at w104.
- Cumulative doses of GC and analgesic use at 28 weeks after randomization and at w104.

B) In the complete study population, including the randomized groups of insufficient responders, each completed with an early responder control population.

Effectiveness:

- Sustained remission = remission for at least 24 weeks (BL-w64, BL-w104, w64-w104).
- Number of treatment changes, number of patients able to follow the protocol, number of patients using biologicals and/or GC throughout the entire study

- Cumulative doses of GC and analgesic use throughout the entire study
- 2. Treatment response in terms of PROs:
 - Patient acceptable symptom state (PASS) and RA Impact of Disease (RAID) at 28 weeks after randomization and at w104
 - PASS at w64 and w104.
 - RAID at w 64, 104.
- 3. Cost-effectiveness:
 - WPAI / EQ5D questionnaire at 28 weeks after randomization and at w104
 - Per-protocol and out-of-protocol medication use as well as the number of outpatient visits and occasional hospitalization

[figure not shown]
Depending on the clinical results of the trial, a health economic analysis may be justified. This could be part of a health technology assessment project at KCE. Quality of life data as well as the national number of the participating patients are collected in this trial to facilitate a possible economic analysis.

3 Study design

Overall design

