In case of an epidemic like the COVID-19 outbreak, the health of patients and coworkers are the first priority. On the other hand, adequate follow-up of patients, with a chronic condition and in need of a chronic treatment, is essential. Interruption of treatment is contraindicated, not for conventional nor for biological or targeted synthetic DMARDs, except in case of active infection or other complications and preferably on the advice of the treating rheumatologist.

Data collected during telephone consultations will be transcribed by the sites at the correct visit page in the e-CRF, marking the box of the telephone visit next to the date field. This way data management can clearly discriminate between data collected by phone and during outpatient consultations.

BL data (w0)

The following information will be captured from routine clinical data (SoC) at Week 0 visit:

- Clinical/Rheumatologic examination
- Joint Count: TJC, SJC
- Weight
- ESR and CRP (in case screening blood samples were taken within 5 days, these values can be used).
- DAS28CRP/DAS28ESR (in case screening blood samples were taken within 5 days, these values can be used)
- VAS PhGA/GH/pain/fatigue
- HAQ
- Relevant concomitant medication
- Relevant side effects
- Changes in employment status

Apart from the above information following PROs will be collected from the patients specifically for the study:

- RAID
- EQ5D/WPAI

Trial assessments

(A schematic overview can be found at page 21)

At week 4, 12, 20, 28, 48, 56, 68, 82, 95 or unscheduled visit following data are captured as part of routine clinical data collection (SoC):

- Clinical/Rheumatologic examination
- Joint Count: TJC, SJC
- Weight
- ESR and CRP
- DAS28CRP/DAS28ESR
- VAS PhGA/GH/pain/fatigue
- Relevant concomitant medication
- Relevant side effects
- Changes in employment status

Randomization procedure is optional and is preferably done at the dedicated visits (w8, 16, 24 or 32). In case randomization is required in between these visits, when LDA is not reached, it is allowed at week 12, 20 and 28.

At week 8, 16, 24, 32, 40, 64, 78 and 91 following data are captured as part of routine clinical data collection (SoC):

- Clinical/Rheumatologic examination
- Changes in co-morbidities assessment (co-morbidity shortlist only at w32)
- Joint Count: TJC, SJC
- ESR and CRP
- DAS28CRP/DAS28ESR
- VAS PhGA/GH/pain/fatigue
- HAQ
- X-ray (Sharp/van der Heijde Score) only for w24 visit
- Relevant concomitant medication

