- Relevant side effects
- Changes in employment status

Apart from the above information following PROs and assessments will be collected specifically for the study at these time points:

- RAID
- EQ5D/WPAI
- PASS (only w64)
- Randomization procedure in case LDA is not reached between w8 and w32, and in case remission is not reached at w32. This randomization procedure will be done preferable at the dedicated time points w8, w16, w24 or w32 but when required is also allowed in between these visits. This can be done with an optional procedure at visit w12, 20 or 28.

At yearly and endpoint visits (week 36, 44, 52, 60 and 104) following data are captured as part of routine clinical data collection (SoC):

- Clinical/Rheumatologic examination
- Joint Count TJC, SJC
- Weight
- Changes in co-morbidities assessment (co-morbidity shortlist only at w52 and 104)
- RF and ACPA status only at w104
- ESR and CRP
- X-Ray hands/feet (Sharp/van der Heijde Score) on a yearly basis
- DAS28CRP/DAS28ESR
- VAS PhGA/GH/pain/fatigue
- HAQ
- Relevant concomitant medication
- Relevant side effects
- Changes in employment status

Apart from the above information following PROs and assessments will be collected specifically for the study at these time points:

- RAID
- EQ5D/WPAI
- PASS (only w52 and 104)

Withdrawal of patients

Any patient may withdraw from the study for any reason at any time. The investigator may withdraw any patient from the study if it is not in the patient's best interest to continue.

In this trial, all included patients will be followed according to the protocol for the complete study period unless they withdraw consent, are lost to follow up or die.

Protocol violations in relation to the therapeutic strategy will not be considered a reason to interrupt follow up within the CareRA2020 study.

In case the proposed treatment schedule cannot be followed due to serious safety concerns, the patient will be kept in the study for further follow up and treated at the discretion of the investigator, taking into account the interest of the patient and the feasibility of the treatment.

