The maximal duration of this study will be 108 weeks (104 weeks of treatment and a maximal interval of 4 weeks between screening and BL)

The enrolment period will be 2 years estimated to start in Q2 2018, so the closure of the recruitment period is estimated at Q2 2020.

The end of the RCT is estimated at Q2 2022 (LPLV, Last patient last visit).

After completing this 2-year randomized controlled trial, all patients will be asked to give their informed consent to continue with a separate 3-year observational follow-up trial.

In case of restrictions in the usual outpatient care organization at the participating rheumatology centers due to governmental or local regulations (e.g. related to the outbreak of an epidemic), the inclusion in this trial will be temporally suspended and it will resume as soon as it is allowed. This will impact the timelines of this trial and will delay the inclusion and "end of trial" timelines for the duration of the suspension period.

Due to the COVID-19 outbreak the inclusion is suspended from 17/03/2020 until governmental and local regulations allow reopening the inclusion.

Study discontinuation

The sponsor may discontinue the study in case of safety concerns or major logistic problems.

Time schedule

The schedule of procedures is summarized at page 22 and in the appendices (page 67). A maximum of 4 weeks is allowed between screening and BL visit (w0). In case a BL visit is done within 5 days of screening, data collected at screening and blood results can be re-used if the investigator expects no change.

Every effort will be made to see patients within a time frame of one week before and one week after the target date until week 64. With the exception of week 8, where no time window before the target date is allowed. From w64 until w104 it is aimed to see patients within two weeks of the target date.

At BL (w0), a list with target dates (+/- window) for each follow up visit will be created within the e-CRF.

In case of restrictions in the usual outpatient care organization at the participating rheumatology centers due to governmental or local regulations (e.g. related to the outbreak of an epidemic), it will not be feasible to have all visits performed within the visit window. Every effort should be made to perform mandatory visits (as outpatient visit or telephone visit) as much as possible within the defined windows. However, getting out of window will not be considered a problem.

8 Trial medication

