
** PRO's: HAQ, VAS scales done in routine; RAID, EQ5D, WPAI, PASS added to evaluate disease specific activity, health economics and patient acceptance, total duration of PRO collection about 10 min.

Flowchart	Screen	Bl	W4	W8	w12	W16	w20	w24	w28	w32	w36	w40	w44	w48	w52	w56	w60	w64
Randomized at W8	x	x	x	x	x	x	x	x	x	x	x	x	x	x	x	x	x	x
Randomized at W16	x	x	x	x	x	x	x	x	x	x	x	x	x	x	x	x	x	x
Randomized at W24	x	x	x	x	x	x	x	x	x	x	x	x	x	x	x	x	x	x
Randomized at W32	x	x	x	x	x	x	x	x	x	x	x	x	x	x	x	x	x	x
Not randomized	x	x	x	x	x	x	x	x	x	x	x	x	x	x	x	x	x	x

General mandatory visit	R+28w
General optional visit	

Mandatory visits for randomized patients	R+24w
	R+16w
	R+8w

Safety Reporting Flow Chart

To be developed based on the final protocol and what is described previously.

Amendment History

Amendment No.	Protocol version no.	Date issued	Author(s) of changes	Details of changes made
0	0.1	17/12/2016	JJ	First draft
0	0.2	02/01/2017	JJ	Second draft with implementation of remarks KCE and CTC
0	0.3	05/01/2017	JJ	Draft after internal discussion RW, JJ and SP
0	0.4	11/01/2017	JJ	Draft after remarks with PV VS SP JJ and AH (CTC)
0	0.5	13/01/2017	JJ	Incorporating remarks PV, VS, PS and JJ
0	0.6	19/01/2017	JJ	update
0	0.7	27/01/2017	JJ	Pre Final draft
0	0.8	31/01/2017	JJ	Final Draft
0	0.9	04/04/2017	JJ	Implementations of remarks KCE, statistical plan included (PV, VS, SP)
0	1.0	05/05/2017	SP, VS, JJ, PV, BVC	Further implementations of remarks KCE, statistical plan included (PV, VS, SP, BVC)
0	1.1	31/07/2017	JJ, SP, VS, KVE, PV	Implementation of remarks KCE
0	1.2	31/07/2017	JJ, SP, VS, KVE, PV	Internal revision Rheumatology
0	1.3	04/09/2017	JJ, PV, KCE	Implementation of remarks KCE
0	1.4	22/09/2017	JJ	Pre-final
0	1.5	30/10/2017	JJ, PV	Revision of the UZ Leuven team
0	1.6	20/11/2017	JJ, PV	Implementation of remarks KCE
0	1.7	14/12/2017	JJ, PV, CTC	Implementation of remarks on Pharmacovigilance (CTC) and economic evaluation
0	1.8	19/12/2017	JJ, PV, CTC	Review
0	1.9	02/01/2018	JJ	
0	2.0	09/01/2018	JJ, PV	Pre final review
0	2.1	11/01/2018	JJ, PV	Final review
0	2.2	25/01/2018	RW, JJ, PV	Final protocol
0	2.3	06/02/2018	JJ	Correction of typo's

0	2.4	26/04/2018	JJ	Information added on request of FAGG/EC
SM001	2.4	26/04/2018	NA	Addition of 5 sites, no adaptations made to the protocol.
SM002	2.4	26/04/2018	NA	Addition of 5 sites, no adaptations made to the protocol.
SM003	2.4	26/04/2018	NA	Addition of 1 site, no adaptation made to the protocol.

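### PASS is an exploratory outcome 28 weeks after randomisation, but the written assessment lists place it there only for patients randomised at week 24 and leave it out at baseline

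*Combined protocol and SAP*

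**What the plan says.** **Outcome.** Section 2, under the other secondary, exploratory outcome measures, specifies "Patient acceptable symptom state (PASS) and RA Impact of Disease (RAID) at 28 weeks after randomization and at w104". The same block also sets PASS at w64 and w104.

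**Assessment lists.** Section 6 (Trial assessments) has three visit lists:

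- The list for w8, w16, w24, w32, w40, w64, w78 and w91 includes PASS at w64 only.
- The endpoint list opens "At yearly and endpoint visits (week 36, 44, 52, 60 and 104) following data are captured". It has RAID at all of these visits but limits PASS: "PASS (only w52 and 104".
- The list that opens "At week 4, 12, 20, 28, 48, 56, 68, 82, 95 or unscheduled visit following data are captured" has no PASS.

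**Baseline.** The overview of baseline measurements in section 10 includes PASS as a dichotomous variable. The week 0 list in section 6 introduces its questionnaires with "Apart from the above information following PROs will be collected from the patients specifically for the study" and then names RAID and EQ5D/WPAI, but not PASS. The screening list does not have it either.

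**Flow chart.** Section 6 opens by sending the reader to the flow chart for timing. The footnote to the chart's PRO row reads "RAID, EQ5D, WPAI, PASS added to evaluate disease specific activity, health economics and patient acceptance", with no restriction to particular weeks.

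**Timing of randomisation.** The dedicated visits are w8, w16, w24 and w32. Section 6 adds: "In case randomization is required in between these visits, when LDA is not reached, it is allowed at week 12, 20 and 28". Under Time schedule in section 7, visits are aimed for "within a time frame of one week before and one week after the target date until week 64".

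**The concern.** PASS and RAID are specified in one sentence of section 2 with the same time points. At the endpoint visits RAID is listed without limit, while PASS is held to two of the five weeks. The word *only* makes this a direct contradiction and not a mere omission: it excludes w36, w44 and w60, three of the four weeks that are R+28w for the dedicated randomisation visits.

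A site that follows the written lists would have PASS at R+28w from one randomisation week alone. Timing of randomisation is a minimisation factor, so those data would come from a single level of that factor and not from the randomised population for which the outcome is specified.

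The nearest other readings cannot stand in. Etanercept in the accelerated-access arm is planned for 24 weeks, so R+28w is 4 weeks after its planned end. The available readings run from R+24w, at that planned end, to R+44w, 20 weeks after it. A patient-reported state that is not asked for at the time cannot be recovered later.

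**Working it through.** **Inputs.** Permitted randomisation weeks (section 6): 8, 12, 16, 20, 24, 28, 32. Listed PASS weeks (section 6): 52, 64, 104. Visit window up to w64 (section 7): one week either side.

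**Step 1. The plan's own R+28w weeks.** Randomisation week + 28: 8 + 28 = 36, 16 + 28 = 44, 24 + 28 = 52, 32 + 28 = 60. These match the RV+28w cells of Table 4 in section 10 and the non-yearly weeks of the endpoint list, plus w52. For in-between randomisation: 12 + 28 = 40, 20 + 28 = 48, 28 + 28 = 56.

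**Step 2. Compare with the listed PASS weeks.** Gap = nearest listed PASS week − R+28w week.

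| Randomised | R+28w | Nearest listed PASS | Gap (weeks) | Time since randomisation |
|---|---|---|---|---|
| w8 | w36 | w52 | +16 | R+44w |
| w12 | w40 | w52 | +12 | R+40w |
| w16 | w44 | w52 | +8 | R+36w |
| w20 | w48 | w52 | +4 | R+32w |
| w24 | w52 | w52 | 0 | R+28w |
| w28 | w56 | w52 | −4 | R+24w |
| w32 | w60 | w64 | +4 | R+32w |

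The only match is w52: 1 of 4 dedicated weeks and 1 of 7 permitted weeks. All six other gaps are at least 4 weeks, so the one-week window adds no match. For w28 randomisation the next later reading is w64, which is 8 weeks late (R+36w). The w64 reading would be R+28w only for randomisation at 64 − 28 = w36, which is not permitted.

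**Step 3. Other R+28w questionnaires.** Section 2 also sets HAQ, RAID and WPAI/EQ5D at R+28w.

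- Weeks 36, 44, 52 and 60 (endpoint list) and w40 (the w8 to w91 list) include all of them.
- Weeks 48 and 56 do not: their list has the VAS scales but no HAQ, RAID or EQ5D/WPAI. This affects randomisation at w20 and w28, 2 of 7 permitted weeks.
- The visit table in section 6 has no row for w12, w20 or w28, so it does not settle the matter.
- DAS28CRP is listed at all seven R+28w weeks.

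**The case against.** The strongest answer is that the flow chart governs. Section 6 refers to it for timing, its PRO footnote includes PASS without a week limit, and the PRO paragraph in section 7 says PASS will be assessed without naming weeks. On that reading, R+28w and baseline may both be covered and the restriction in the lists is a drafting slip. Questionnaires are delivered by app or web, and the patient schedule is shown in the e-CRF, so sites need not work from the written bullets.

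Much of this stands. It would be wrong to say that the documents give no guidance on where to look for timing. But the pointer to the chart is not an explicit precedence rule, and the footnote does not assign PASS to particular visits. If the chart governs, the restrictions in the lists are wrong. If the lists govern, the R+28w outcome can be met only for w24 randomisation. A correction is needed either way.

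The baseline point is weaker. The baseline list contains no *only*, and section 10 describes its table as variables gathered when COBRA-Slim starts, so the plan does state an intention to collect PASS then. It is an omission from one list.

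A reader might go further and infer any of the following, which the documents do not support:

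- **PASS will be missing at R+28w for three quarters of randomised patients.** The count is of randomisation weeks, not patients. The documents give no split of patients by week and do not show the e-CRF content.
- **Baseline PASS will certainly not exist.** That holds only if the week 0 list is read as exhaustive and section 10 and the chart are set aside.
- **The main secondary outcome is affected.** It uses DAS28CRP, which is listed at every R+28w week.

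**Conclusion.** The contradiction between the outcome definition and the assessment lists holds. Read as written, the lists put PASS on R+28w for 1 of 4 dedicated randomisation weeks (1 of 7 permitted). The nearest reading is otherwise 4 to 16 weeks off target. A planned baseline variable is also missing from the baseline list. The chart and the lists disagree, and what is actually collected cannot be determined from the documents.

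The size is small. PASS at R+28w is exploratory, and such outcomes are reported with confidence intervals without significance claims. PASS at w64 and w104 agrees with the lists. The related gap at w48 and w56 touches HAQ (an other secondary outcome), RAID and EQ5D/WPAI, for in-between randomisation at w20 or w28 only. Nothing here bears on power, the primary outcome or the main secondary outcome. It is a minor reconciliation, worth making because the loss would be irrecoverable if sites or the e-CRF follow the lists.

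The conclusion assumes target visit weeks and the one-week window, and takes the word *only* in the lists at face value.

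**What to change.** 1. In section 6, replace the two restrictions so that PASS is collected at each patient's R+28w visit (w36, w44, w52 or w60; w40, w48 or w56 for in-between randomisation) as well as at w52, w64 and w104.
2. Add PASS to the week 0 list, or delete it from the baseline table in section 10.
3. Align the section 6 lists with the flow chart's PRO row and footnote, and check that the e-CRF and app schedule agree.
4. State that the R+28w questionnaires (HAQ, RAID, EQ5D/WPAI and PASS) follow the actual randomisation week, with w12, w20 and w28 included, and show these weeks in the visit table.

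The cost is one short questionnaire at existing visits and a clarification of the e-CRF schedule. Patients randomised at w20 or w28 would also complete the R+28w questionnaires at w48 or w56.
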